Treatment Description	Forty-five patients undergoing TP-IAT (day 0) at a single center will be randomized 1:1:1 to receive during the peri-operative period either: 1) etanercept (50 mg on day 0 SQ; 25 mg SQ on days 3, 7, 10, 14, and 21), 2) alpha-1 antitrypsin (90 mg/kg IV infusion on days -1, and +3, 7, 14, 21, and 28 post-transplant) or 3) standard care .
Study Procedures	
Patients will be seen within 4 weeks prior to surgery (screening/baseline), and at day 90 (\pm 14 days), day 365 (\pm 28 days), and day 730 (\pm 56 days) post-transplant. These will occur over two days. The following metabolic testing will be performed at each visit:
 
 1) 10 minute IV glucose tolerance test 2) Glucose potentiated arginine induced insulin secretion (GPAIS), performed on same morning as the IVGTT 3) Mixed meal tolerance test (2 hour, Boost HP) 
In addition, patients will have serum draws for mechanistic assessments and safety labs in the first month post-transplant as detailed in the protocol. The mechanistic assessments will include unmethylated insulin DNA and cytokine/chemokine profiles. For long-term follow up of participants, patients will receive routine care subsequent to the day 730 visit, which includes a HbA1c and mixed meal test at yearly intervals. Study investigators will review results from these annual labs and have a telephone follow up with the participant at years 3, 4 and 5 for insulin requirements, blood glucose review, and hypoglycemia history.

Study Abstract

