SPECIFIC AIM #1: To determine if anti-inflammatory treatment with etanercept or alpha-1 antitrypsin during the critical peri-transplant engraftment period improves islet engraftment and function after islet autotransplant, as assessed by area under the curve for C-peptide on mixed meal tolerance testing (oral stimuli), acute insulin response to glucose-potentiated arginine stimulation (IV stimuli), and insulin requirements at day 90 post-transplant. The primary endpoint of the maximally stimulated acute insulin response to arginine (AIRmax) from GPAIS at day 90 will allow us to rapidly identify the most promising therapeutic agent for further development and testing in a large randomized trial.

SPECIFIC AIM #2: To gather pilot data on the long-term impact of etanercept or alpha-1 antitrypsin administered during the peri-transplant period by evaluating islet function at 1 and 2 years post-transplant, as assessed by area under the curve for C-peptide on mixed meal tolerance testing (oral stimuli), acute insulin response to glucose-potentiated arginine stimulation (IV stimuli), and insulin requirements (units/kg/day) at 1 year post-TPIAT. In addition, insulin requirements and fasting/stimulated C-peptide by MMTT will be assessed at yearly intervals from year 3-5 post-transplant.

SPECIFIC AIM #3: To evaluate the mechanistic effects of etanercept and alpha-1 antitrypsin on inflammation, islet cell viability/survival, and beta cell apoptosis. This will be assessed by circulating cytokine and chemokine levels and measurement of circulating unmethylated DNA (a recently validated marker of beta cell death in T1DM) in patient serum.

The **goal** of the current research is to select the anti-inflammatory agent with the greatest potential to preserve islet mass early after TPIAT.

[figure not shown]
STUDY DESIGN OVERVIEW

Overview of Clinical Trial Design for All Aims

In this randomized, controlled non-masked trial, 45 patients age 18-65 years with chronic pancreatitis who are accepted for TPIAT procedure based on standard clinical criteria will be enrolled and randomized 1:1:1 to three study arms:

- 1) Alpha-1 antitrypsin (A1AT), 90 mg/kg/week IV, administered days -1, and +3, 7, 14, 21, and 28.
- 2) Etanercept administered as 50 mg SQ prior to the islet infusion (day 0) and 25 mg SQ on days 3, 7, 10, 14, 21 post-transplant.
- 3) Standard TPIAT care

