Patients will be seen in follow up at 90 days and 1 year post-transplant for metabolic testing. The maximally stimulated acute insulin response (AIRmax) obtained from glucose potentiated arginine-induced insulin secretion (GPAIS) at 90 days post-transplant is the primary endpoint for the study. AIRmax has previously been demonstrated to correlate best with islet mass in human and animal models; by assessing AIRmax at 90 days post-transplant, we will be able to rapidly evaluate the therapeutic impact of these agents and select the agent most promising for further study and development. Mechanistic studies will be performed frequently throughout the early transplant period. Inflammatory cytokines will be measured by repeated serum sampling in the first 1 week post-transplant. Unmethylated insulin DNA levels will be monitored in the first 1 month post-transplant. Insulin requirements and fingerstick blood glucoses will be monitored throughout the study duration. Key secondary endpoints include the area under the curve (AUC) for C-peptide from mixed meal tolerance testing, the acute insulin response (AIRglu) on IV glucose tolerance test, the acute C-peptide response to glucose (ACRglu) on IVGTT, and the maximally stimulated C-peptide response (ACRmax) from GPAIS at day 90 and 1 and 2 years, and the AIRmax at 1 and 2 years, as well as average daily insulin requirements at each time point. As an exploratory component, we will continue to collect the basic clinically available measures of insulin use/dose, HbA1c, and simple fasting and stimulated glucose and C-peptide from a mixed meal test annually for years 3-5 post-transplant, all part of the patients' routine cares.

Study Treatment

Study drugs: The two investigational agents administered in this study are as follows:

- 1) Alpha-1 antitrypsin (Aralast NP) intravenously at a dose of 90 mg/kg IV weekly. Treatment will be started 1 day prior to surgery and on days +3, 7, 14, 21, and 28 after infusion. This is infused as a rate of no more than 0.2 mL/kg body weight/minute, and may be slowed depending on patient tolerability.
- 2) Etanercept: dosing in adult recipients is 50 mg SQ on day 0, and 25 mg SQ on days 3, 7, 10, 14, 21.

All medication doses will be administered in the hospital (during post-operative hospitalization) or in the research center by an RN.

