A local follow up with telephone or face-to-face encounter to review insulin requirements, blood glucose logs, and obtain local mixed meal tolerance test results (part of standard clinical care) will occur at years 3, 4, and 5 (all \pm 2 months) for exploratory data on long-term efficacy. This information will be readily available, as it is part of the standard routine care of all TPIAT recipients at UM.

Subject screening visit

Subjects’ medical history will be reviewed from the electronic medical record and from history obtained from the patient to confirm eligibility. In addition, the following screening assessments will be performed at a screening visit within 4 weeks prior to the scheduled surgery date, after informed consent has been obtained:

- Complete metabolic battery (includes hepatic panel, creatinine, fasting glucose)
- CBC with differential and platelets
- Urine pregnancy test in women with child-bearing potential (if \geq 7 days since screen, repeat prior to first dose of study drug administration; UPT not necessary in females s/p hysterectomy procedure)
- Hepatitis C and hepatitis B serology, HIV ELISA
- IgA level
- Mantoux skin test or Quantiferon (serum) for TB screening
- Hemoglobin A1c level
- Mixed Meal Tolerance Test
- IV glucose tolerance test
- Glucose potentiated arginine-induced insulin secretion

Table. Study Flowchart (year 0-2)

	screening	Days 0-7	Days 7, 14, 21, 28	Day 60	Day 90	Day 365 (Year 1)	Day 730 (Year 2)
Study Visit Assessments (abbreviated)							
Insulin Use/Dose (u/kg/day, endpoint)			X		X	X	X
Mixed Meal Tolerance Test (AUC C-)	X				X	X	X
IVGTT (AIRglu, ACRglu)	X				X	X	X
GPAIS (AIRmax, ACRmax)	X				X	X	X
HbA1c level	X				X	X	X
iPro2 (6 day CGM)					X	X	X
Complete metabolic panel, CBC	X		X*		X	X	X
Random morning C-peptide and glucose			Day 7, 14				
Fasting glucose, C-peptide, creatinine	X		Day 28		X	X	X
Drug safety assessments (PE, hx, labs)		X	X				
Inflammatory cytokines (see text)**		X					
Unmethylated insulin DNA levels**		X	X				
Safety assessment (phone visit for symptoms)				X			
Islet Assessments (see text)		Day 0					

* **Years 3, 4, and 5:** Telephone or face-to-face review of insulin use/dose; labs (HbA1c, clinical MMTT)

** Drawn at multiple time points, as detailed in the methods for Specific Aim #3.

Design and Methods to Evaluate Specific Aim #1

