In addition, at 90 days post-transplant, patients will have a fasting C-peptide and fasting glucose drawn (as part of MMTT), to calculate basic measures of early function, including: 1) Fasting C-peptide to glucose ratio; and 2) SUITO index (calculated as fasting C-peptide [ng/ml] / (fasting blood glucose - 63 [mg/dl]) $\times 1500$) (78). In addition, a random glucose and C-peptide level are obtained at day 7, 14, and day 28 after surgery.

In between visits at the study center, patients will be asked to continually maintain a log of self-monitored blood glucoses and insulin doses. Patients will be instructed to check fingerstick blood glucose at least 4 times per day (pre-meal and bedtime). Patients will be instructed to send logs to the study PI and coordinator at least once monthly for adjustment of insulin dosing. Insulin doses are adjusted by the PI based on site standard protocol, to maintain the following goals: fasting glucose <126 mg/dL, 2 hours after a meal <180 mg/dL, and HbA1c $\leq 6.5\%$. Patients have HbA1c levels drawn quarterly for clinical monitoring (standard of care). Any patient not meeting these goals off insulin is not considered insulin independent per protocol.

Safety monitoring: The PI and study coordinators will monitor for adverse events throughout the study period, as described in the human subjects monitoring plan. The coordinator or investigator will collect a history for safety assessment at day 60 (may be done by telephone visit if patient is not able to return to study center). Additional monitoring for safety will include history at each scheduled visit day 0- 30 for symptoms of DVT or PE (using Wells criteria) with lower extremity ultrasound or spiral CT performed if response moderately to highly suspicious for deep vein thrombosis (DVT) in the lower extremities (Well's >2) or pulmonary embolism (PE) (Well's >4) respectively. Note that in this population all patients are expected to have a Wells score of 3 (meets 'moderate' suspicion threshold) as 100% are immobilized and nearly 100% have intermittent tachycardia from pain and thus a score of 4 or greater will be achieved only in the context of symptoms to suggest PE. Likewise, the Well's score of >2 accounts for the surgery, immobilization and bilateral lower edema swelling (normal post-TPIAT) that will occur in all patients. At day 60, the telephone encounter will include assessment of symptoms for PE or DVT. An EKG will be performed at baseline, day 28 and day 90.

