If the treatment is successful, the potential benefit of the study treatment is significant, including potential for reduced incidence of diabetes, or better controlled diabetes after surgery. The total pancreatectomy and islet autotransplant is a major surgical procedure. Minor complications (including nausea/ vomiting, delayed gastric emptying, pain) are not uncommon and recovery is gradual. There is a high risk of partial or total diabetes. A1AT or etanercept used only temporarily, and have relatively few safety risks over this short duration of treatment. Thus, we expect the additional study treatment to contribute only minor risks compared to the overall risks of the total pancreatectomy and islet autotransplant.

Other benefits: The knowledge gained from the extensive metabolic and islet graft assessments performed in this trial will advance the understanding of islet autotransplantation.

ADVERSE EVENT DOCUMENTATION AND TERMINATION CRITERIA

Adverse events: All adverse events will be recorded for all subjects, and graded according to the CTCAE version 4.0. All AEs, regardless of severity will be collected from day 0 to the day 90 visit (drug exposure window). Subsequent to day 90, only severe AE's (as subsequently defined) are collected, from day 90 to the final face to face visit at day 730. AE's include new or worsening symptoms reported by the subject, signs on physical exam (performed at each study visit), and/or abnormalities on study labs. AE's will be reviewed by the DSMB as described in the section below. Serious adverse events will be reported to the IRB per institutional guidelines (within 10 days for an event that meets rapid reporting requirements), and to the DSMB and the FDA within 72 hours in accordance with IND regulations.

Each event will be analyzed to determine its relatedness to study medication (definitely, probably, possibly, unlikely, or unrelated) and the severity will be graded as follows, modified from the Common Toxicity Criteria:

- MILD (Grade 1) – transient or mild discomfort; no limitation in activity; no medical intervention required.
- MODERATE (Grade 2) – mild to moderate limitation in activity, some assistance may be needed; no or minimal medical intervention/therapy required.
- SEVERE (Grade 3) – marked limitation in activity, some assistance usually required; medical intervention/therapy required, hospitalization is possible.

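### All-grade adverse event collection opens on day 0 in every arm, but A1AT dosing starts on day -1, so each A1AT patient's first dose day lies outside the stated drug exposure window.

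*Combined protocol and SAP*

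**What the plan says.** The section Adverse Event Documentation and Termination Criteria sets one explicit window for events of every grade: "All AEs, regardless of severity will be collected from day 0 to the day 90 visit (drug exposure window"). After the day 90 visit only severe events are collected, to day 730. The window has no arm-specific start. The sentence just before it is general: "All adverse events will be recorded for all subjects, and graded according to the CTCAE version 4.0". The safety monitoring paragraph under Specific Aim #1 is also general: "The PI and study coordinators will monitor for adverse events throughout the study period, as described in the human subjects monitoring plan".

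The synopsis (Treatment Description) fixes the time origin: "Forty-five patients undergoing TP-IAT (day 0) at a single center will be randomized 1:1:1". It then gives the A1AT schedule: "alpha-1 antitrypsin (90 mg/kg IV infusion on days -1, and +3, 7, 14, 21, and 28 post-transplant"). The Study Treatment section repeats the early start: "Treatment will be started 1 day prior to surgery and on days +3, 7, 14, 21, and 28 after infusion". The Study Design Overview places the first etanercept dose on the transplant day: "Etanercept administered as 50 mg SQ prior to the islet infusion (day 0"). The drug administration rows of the visit schedule agree, with A1AT first given on day -1 and etanercept on day 0.

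**The concern.** The window is described as covering drug exposure, yet it opens one day after A1AT exposure begins. A day -1 event is outside it in any arm, but only in the A1AT arm is day -1 on-drug time.

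The Background says the two drugs are compared partly to choose the one with the better balance of benefit and risk, so the safety record should cover every dose of both. Any drug-related events lost through this gap can come only from the A1AT arm. Day -1 is also the only A1AT dose given before surgery. The protocol notes that hypotension and tachycardia are common just after the operation, and that nausea and pain are not uncommon during recovery. I infer that a reaction on day -1 would be among the easiest to attribute to drug.

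**Working it through.** The plan gives no figure to reproduce here. The check compares dates and then bounds the number of events that could be lost.

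**Dose days against the window.** The window runs from day 0 to the day 90 visit. That visit can fall between day 75 and day 105 (±15 days in the Aim #1 methods and the visit schedule; ±14 in the synopsis gives day 76 as the earliest). The result is the same for a visit on day 75, 76, 90 or 105.

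| Arm | Planned dose days | Outside the window |
|---|---|---|
| A1AT | -1, 3, 7, 14, 21, 28 | day -1 (1 of 6) |
| Etanercept | 0, 3, 7, 10, 14, 21 | none (0 of 6) |
| Standard care | none | not applicable |

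- With 45 patients, 45/3 = 15 per arm and 15 × 6 = 90 doses per drug arm. Outside the window: 15/90 = 16.7% for A1AT, 0/90 for etanercept.
- With 48 randomized (Accrual Objective), 48/3 = 16 per arm: 16/96 = 16.7% against 0/96.

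**Do the schedules close the gap?** They do not. In the flowchart, the row "Drug safety assessments (PE, hx, labs") is first marked under days 0-7. In the visit schedule, the AE assessment row is marked at days 7, 14, 21, 28, 90, 365 and 730, with nothing in the column for day -1 or 0.

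**Expected events lost.** The risk table under Potential Risks and Benefits does not say whether its A1AT rates are per infusion or per patient, so I show two readings for 15 patients. Reading A applies the whole rate p to the first infusion (q = p). Reading B spreads it evenly over a six-dose course (q = p/6). Both assume that every event stays within day -1, which overstates the loss. The expected count is 15q, and the chance of at least one is 1 - (1 - q)^15.

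| Event (stated rate) | Reading B: expected, chance of ≥1 | Reading A: expected, chance of ≥1 |
|---|---|---|
| Infusion reaction (0.1%) | 0.0025, 0.25% | 0.015, 1.5% |
| Headache, low end (0.3%) | 0.0075, 0.75% | 0.045, 4.4% |
| Pruritus (1%) | 0.025, 2.5% | 0.15, 14.0% |
| Rash (1.5%) | 0.0375, 3.7% | 0.225, 20.3% |
| Headache, high end (7%) | 0.175, 16.1% | 1.05, 66.3% |

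With 16 patients, infusion reactions give 0.0027 to 0.016 expected and headache at 7% gives 0.187 to 1.12. These are expected counts, not maxima.

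**After the change.** With collection opening on day -1, all 6 of 6 A1AT dose days fall inside the window. Etanercept is 6 of 6 either way.

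**The case against.** The strongest reply is that the text is loose rather than wrong. The preceding sentence promises that all events are recorded, the Aim #1 text promises monitoring throughout the study, and the label on the window shows an intent to cover exposure. The visit schedule merges day -1 and day 0 into one column, so day 0 may be shorthand for that visit. This has some force, and staff might well record a day -1 reaction. But neither general statement gives a start day. The first cannot be an unlimited rule, because the same paragraph restricts collection after day 90. The synopsis and the dosing rows also treat day -1 and day 0 as different days.

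The schedule evidence is supporting only. The flowchart is abbreviated and has no day -1 column. The AE row starts at day 7 for all arms, so it also lacks marks for etanercept on days 0 and 3, which are inside the window.

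The practical effect is small, and this stands in full. Serious event reporting has no day 0 start, and the definition of a serious event is broad. A nurse gives every dose on site with an investigator on call. Events that persist or worsen into day 0 are inside the window. The high headache figure takes the top of a wide range and puts all of it on the first infusion.

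Finally, the human subjects monitoring plan and the text that follows the termination rules were not available to me, and either could state a different start.

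**Conclusion.** The concern holds, as a minor one. The only explicit all-grade window starts after the first A1AT dose. On the planned schedule it leaves out one sixth of A1AT doses, all of them first exposures, and no etanercept dose. I am confident of that reading of the sentence, moderately confident that staff would apply it literally, and do not expect many events to be lost. For infusion reactions, the chance of losing one is at most about 1.5% on the stated rate.

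The effect is confined to the descriptive safety record and what the DSMB reviews. The primary endpoint and stopping rules are untouched, and the analysis section plans no between-arm test of adverse events. Objectives and Specific Aims bases the choice of drug on mechanistic data and day 90 graft function.

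The conclusion assumes doses are given on their planned days; they may be held and resumed, with no stated last day. It rests only on the day 0 start. The exposure label is also loose at the other end, since planned dosing stops on day 21 or 28, but that loses nothing.

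**What to change.** Open all-grade collection at one common point, at or before the first possible dose of either drug (for example the start of day -1), in all three arms, and run it to the day 90 visit. Reword the exposure label to match.

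Mark an AE assessment in the visit schedule column for day -1 or 0. That column is required only for the two drug arms, so ask standard-care patients about day -1 at the transplant visit. Moving the start date alone would close the gap; the mark and the question keep ascertainment equal between arms. If the monitoring plan already gives an earlier start, align the protocol sentence with it.

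The cost is a one-line amendment, one schedule mark and one extra question for standard-care patients. Staff are already present at each dose, and nothing about dosing changes.

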- Insulin levels (GPAIS and IVGTT): To obtain accurate results in this population, we require an insulin assay that is resistant to interference from hemolysis. Fairview does not offer an adequate assay for this purpose. We will ship serum for insulin levels to the Northwest Lipid Research Laboratories at the University of Washington. Timed test glucose and C-peptide measures will also be run at NWLRL due to their ability to handle such timed, repeated measures specimens.
- Unmethylated insulin DNA: This specialized assay will be run by [name] lab at Yale University
- Trypsinogen, TAP, and liver injury markers: ELISA kits for the respective assays will be purchased and the laboratory assessments run by the technician in [name] lab.

For labs that require shipping, all specimens are labeled with the study ID number and contain no identifying information. Specimens are shipped overnight by FedEx on dry ice. All study personnel performing specimen shipping are trained in shipping through a session offered to research staff at the University of Minnesota. Appropriate precautions and labeling for biohazard materials are undertaken.

Visit Day	Screening	Day -1 or 0	Transplant visit*	Day 3	Day 7	Day 10	Day 14	Day 21**	Day 28**	Day 60	Day 90	Day 365	Day 730
Visit window	N/A	N/A	N/A	N/A	N/A	N/A	N/A	± 1	± 1	± 7	± 15	± 28	± 56
Req'd for Tx arms:	ALL	Etan/ A1AT	ALL	ALL	ALL	Etan	ALL	ALL	ALL	ALL	ALL	ALL	ALL
General Assessments													
Informed Consent	X												
History	X				X		X		X	X	X	X	X
Physical Exam	X				X		X		X	X	X	X	X
Hypoglycemia History											X	X	X
Insulin use (patient records), u/kg/day											X	X	X
AE assessment					X		X	X	X		X	X	X
Basic Labs/Safety													
Complete metabolic panel	X				X		X	X	X		X	X	X
CBC with plt/diff	X				X		X	X	X		X	X	X
D-dimer (safety assessment)	X		X	X	X		X	X	X				
IgA level	X												
Hepatitis B sAg and Ab	X												
Hepatitis C Ab	X												
HIV ELISA	X												
Urine pregnancy test (Fm)	X												
Manitoux skin test or Quantiferon (TB)	X												
Hemoglobin A1c	X										Quarterly through study		
EKG	X									X	X		
Metabolic Assessments													
Mixed meal test	X										X	X	X
GPAIS	X										X	X	X
IV glucose tolerance test	X										X	X	X
Continuous glucose monitor (iPro)											X	X	X
C-peptide: glucose (fasting)											X		
C-peptide and glucose (random)						X		X		X			
Mechanistic Assessments													
Inflammatory Cytokines*			X	X	X								
Unmethylated insulin DNA*			X	X	X		X	X	X		X	X	X
Serum trypsin and urine TAP*			X										
A1AT levels	X	X			X		X	X	X				
Liver injury markers*			X	X	X								
Study Drug Administration													
Etanercept (only for Etan. arm)		day 0		X	X	X	X	X					
A1AT (only in A1AT arm)		day -1		X	X		X	X	X				

* These mechanistic assessments during "transplant visit" include multiple draws. Please refer to text in protocol for specific times of draw.

Patients will be inpatient per usual clinical care through day 7 at minimum.

** +/-1 day window for labs and assessments. Study drug should be given on day 21 and day 28 whenever possible for consistency.

References

